## STUDY MATERIALS

### Provided to each site

- INDICAID COVID-19 Rapid Antigen Test kits labeled “For Investigative Use Only”.
- INDICAID COVID-19 Rapid Antigen Test Quick Reference Guide
- Contrived samples for testing (10 positive and 10 negative)
- Clinical study materials, forms, and templates

### Materials Needed (at each site)

- Sample collection kit (comparator FDA EUA RT-PCR test)

## STUDY PROCEDURES

### Informed Consent

In order to protect the rights, safety, and welfare of subjects, the study is conducted in accordance with the 21 CFR 50, Protection of Human Subjects. Prior to study enrollment, each subject will be asked to voluntarily provide his or her oral consent after being provided the IRB-approved Research Information Sheet. The Investigator or designee will explain the nature, purpose, expected duration, and risks of study participation. Each potential subject will have the opportunity to ask questions and receive answers from personnel conducting the study. All subjects will be provided a copy of the Research Information Sheet.

### Study Participant Enrollment and Eligibility Criteria

Study participants must meet the eligibility criteria listed below in order to be enrolled in the study.

#### Inclusion Criteria

- Study participant has provided verbal informed consent as required by reviewing institutional review board (IRB). The Experimental Bill of Rights will also be provided for all study participants enrolled in applicable states.
- Study participant is at least 5 years of age. Participants under 18 years old requires parental/legal care provider consent.
- Study participant reports at least 2 of the following COVID-19 symptoms:
  - Fever or chills
  - Fatigue
  - Sore throat
  - Congestion or runny nose
  - Cough
  - Headache
  - Diarrhea
  - Shortness of breath or difficulty breathing
  - Muscle or body aches
  - New loss of taste or smell
  - Nausea or vomiting
- On-set of symptoms must be within 7 days.
- Study participant has been previously tested with an FDA EUA SARS-CoV-2 Antigen test as part of the clinic site standard of care and with test results known.
- Study participant agrees to provide the following specimens for this study:
  - Three (3) clinician-collected nasal swabs (two swabs to perform sequential INDICAID Rapid Tests and a third to perform the comparator FDA EUA RT-PCR test. See below for sample collection instructions)

### Exclusion Criteria

- The study participant has been previously enrolled to the study
- Participant is under the age of 5 years
- Participant does not consent
- Participant cannot provide the required samples
- Patient is asymptomatic

### Specimen De-Identification

Study specimens will be identified by a study-specific ID number and will not contain any additional protected health information (PHI).

### Study Participant Withdrawn or Excluded After Enrollment

If, after enrollment, a study participant is found to have not met an inclusion criterion, the study participant will be withdrawn from the study and any completed test results will be excluded from data analyses.

### Operator Background

All study operators are to be non-laboratory, healthcare professional personnel. Between the 2 sites a minimum of 5 operators shall be enrolled to perform the testing.

### Order of Specimen Collection

Specimen collection for testing with the INDICAID Rapid Test and the comparator RT-PCR test will take place after standard of care and will be randomly assigned.

### INDICAID Specimen Collection and Testing Procedure

- INDICAID Rapid Test specimens will be collected and tested according to the INDICAID COVID-19 Rapid Antigen Test Quick Reference Guide.
- Each operator shall test a minimum of 3 positives and 3 negatives
- Operator ID, Patient ID, Date of Collection and test results (presence or absence of Control Line and Test Line and positive or negative results interpretation) are to be recorded on the Data Collection Form provided.
- INDICAID Rapid Test results will not be disclosed to the patient. COVID-19 disease state will be based on the Standard of Care procedures at the clinical site.

### Comparator Test Specimen Collection and Testing Procedure

- Comparator FDA EUA RT-PCR test specimens will be collected and shipped to a CLIA certified laboratory, Warrior Diagnostics, Loveland Colorado (or equivalent site and method to be approved by Phase Diagnostics) according to the sites' Standard of Care procedures for RT-PCR Testing.
- Operator ID, Patient ID, Date of Collection and results from the laboratory testing service provider are to be recorded on the Data Collection Form.

- Comparator test results will not be disclosed to the patient. COVID-19 disease state will be based on the Standard of Care procedures at the clinical site.

#### Bias Minimization and Elimination

To minimize bias in specimen analysis by the INDICAID Rapid test, the following practices will be employed:

- Each site will be identified with a numerical ID code
- Patients eligible for the study will be screened by a separate clinic personnel not involved in collecting patient samples or performing the INDICAID Rapid Test.
- Operators collecting the patient samples and performing the INDICAID Rapid Test shall be blinded to the result of any prior rapid antigen test or comparator RT-PCR test.

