#### PRINCIPLE OF TEST

The INDICAID Rapid Test is a chromatographic rapid test (approximately 20 minutes) that uses a sandwich immunoassay design to directly and qualitatively detect the presence or absence of SARS-CoV-2 nucleocapsid protein. The results of the test are visually interpreted.

After collecting the swab, the patient's sample is placed in the Buffer Solution Vial containing an extraction buffer. The sample is dispensed into the sample well of the test device and migrates through the test strip that contains antibodies conjugated to a chromophore (detector particle). This antibody-chromophore conjugate will bind to the nucleocapsid protein of the SARS-CoV-2 virus if present in the sample. The sample continues to flow through the test strip and is trapped by capture antibodies, which can be visually observed by the presence of the test line ("T").

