### Sample Enrichment

In order to enrich for positive patient samples, we will be enrolling patients who have previously been tested with an FDA EUA approved Antigen Test until we obtain the required 30 positive and 30 negative specimens (as tested by the comparator RT-PCR test).

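### Operators must be blind to the prior antigen result, but nothing stops a participant who knows it from telling the operator before the visual read, and no field records whether that happened

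*Combined protocol and SAP*

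**What the plan says.** All references are to the combined protocol and SAP.

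- **The rule.** Bias Minimization and Elimination: "Operators collecting the patient samples and performing the INDICAID Rapid Test shall be blinded to the result of any prior rapid antigen test". The same sentence extends the blind to the RT-PCR result.
- **The safeguard.** The same section: "Patients eligible for the study will be screened by a separate clinic personnel not involved in collecting patient samples or performing the INDICAID Rapid Test". The remaining item there, a numerical site code, has no bearing on what an operator learns about a participant.
- **Who has a prior result.** Everyone. Inclusion Criteria require an earlier antigen test "as part of the clinic site standard of care and with test results known", and Sample Enrichment makes this the recruitment route: "In order to enrich for positive patient samples, we will be enrolling patients who have previously been tested with an FDA EUA approved Antigen Test".
- **Contact with the participant.** Inclusion Criteria specify three nasal swabs collected by a clinician, two of them for INDICAID. Under Order of Specimen Collection, this "will take place after standard of care and will be randomly assigned".
- **The read.** Principle of Test: "The results of the test are visually interpreted".
- **What is kept from the participant.** The INDICAID and comparator procedure sections withhold those two results. No section withholds the prior antigen result, and both sections leave disease state to the site's standard of care.
- **What is recorded.** The INDICAID procedure section lists operator and patient identifiers, collection date, presence of each line, and the interpretation.
- **Breaches in general.** Protocol Deviations requires unplanned deviations to be documented and reported, and the sponsor to judge their effect on validity.

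**The concern.** The protocol itself treats knowledge of the prior antigen result as a source of bias, and rightly so. That result comes from a test for the same virus, and the plan relies on such testing to enrich for RT-PCR positives. An operator who has heard it and then faces a faint test line has an answer to lean on.

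The result can reach the operator through staff or through the participant. A separate screener closes the staff route. The participant route stays open: every listed step can be followed to the letter while the participant, sitting for the swab, mentions the earlier result. At stake is whether the reported PPA and NPA reflect the device alone or the device plus prior information, and whether the sponsor could later show which. Whether an operator knew the result cannot be reliably reconstructed after the study.

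**Working it through.** **1. Procedural check.** Four conditions must all hold for the blind to fail through the participant.

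| Condition | What the documents support |
|---|---|
| A prior result exists | Stated, for every participant (Inclusion Criteria, Sample Enrichment) |
| The participant knows it | Inferred. The criterion says results are known, not to whom. It is a standard-of-care test, and no section withholds it |
| The person who reads has met the participant | Natural reading. Collecting and testing are described as one operator role, but no sentence says the same person always does both for a given patient |
| Nothing prevents or records disclosure | No instruction to participants and no form item appears in the documents. General deviation reporting applies if someone recognises and reports the breach |

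The failure is therefore possible under full compliance with the listed steps. How often it would occur is not given.

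**2. Scale of one read.** The plan's figure is a minimum of 30 RT-PCR positives and 30 negatives (Study Overview). No expected PPA or NPA, target or margin accompanies it, so there is no calculation to reproduce. Assuming one INDICAID result per participant enters the two-by-two table, one changed read moves PPA or NPA by 1/30 = 3.3 points.

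The plan's interval is the 95% Wilson score interval, with z = 1.96:

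centre = (p + z²/2n) / (1 + z²/n); half-width = z × √[p(1−p)/n + z²/4n²] / (1 + z²/n)

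- 24/30: p = 0.800, centre 0.766, half-width 0.139, giving 80.0% (62.7 to 90.5).
- 26/30: p = 0.867, centre 0.825, half-width 0.122, giving 86.7% (70.3 to 94.7).

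Two faint lines called positive instead of negative would raise PPA by 6.7 points and its lower limit by 70.3 − 62.7 = 7.6 points. The starting count of 24 is illustrative.

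**3. Direction.** The pull is toward the prior antigen result, not toward RT-PCR. Let f be the share of RT-PCR positives with a faint line and s the share of those whose prior result was positive. Assume, purely for illustration, that a faint line is called positive with probability 0.60 when masked, 0.90 when the operator knows of a positive prior result, and 0.30 when the operator knows of a negative one. With every read unmasked:

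PPA shift = f × [s × (0.90 − 0.60) + (1 − s) × (0.30 − 0.60)] = f × 0.30 × (2s − 1)

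At f = 0.30:

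- s = 0.9: 0.30 × 0.30 × 0.8 = +7.2 points
- s = 0.7: 0.30 × 0.30 × 0.4 = +3.6 points
- s = 0.5: 0
- s = 0.4: 0.30 × 0.30 × (−0.2) = −1.8 points

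If only a share u of reads is unmasked, each figure is multiplied by u. The same logic applies to NPA, with s as the share of faint-line RT-PCR negatives whose prior result was negative. None of f, s, u or the call probabilities is in the documents, so neither sign nor size can be derived from them.

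**The case against.** The case against has real force.

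- **The blind is already mandatory.** A disclosure would breach it and fall under Protocol Deviations, and the operator who hears the result is the person who would know. This stands against any claim that the leak is undetectable. But that route depends on someone recognising a remark as a deviation and reporting it. Nothing prompts the operator to do so.
- **Training and unseen material.** Site initiation and protocol training are required, and a hand-over script could sit in the study forms or the Research Information Sheet, neither of which is included here. That is possible. If a script exists, the protocol should cite it.
- **Two premises are inferences.** Participant knowledge of the result, and one person both swabbing and reading, are readings of the text. This stands, and the point is worded as a possibility for that reason.
- **The remedy has the same weakness.** A tick box also relies on self-report, and a subset of about 30 per group would rarely separate a shift of a few points. This stands too, but a direct question asked each time is more reliable than an unprompted report.

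A reader might also infer that the line is read as soon as the swab is taken. Storage Handling and Shipment says specimens are tested immediately. The result itself takes 15 minutes (Background / Rationale) or about 20 (Principle of Test).

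**Conclusion.** The gap is real but modest. The protocol states a blinding rule and protects it on the staff side only. A participant who knows the prior result could disclose it before a visual read, and the listed data would not show that this had happened. This rests on the two inferences set out in the check.

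A reader might go further and conclude that PPA and NPA are both inflated. The documents do not support that. Drift follows the prior antigen result, so it raises agreement only where that result matches RT-PCR. Samples that give faint lines may also be ones an earlier antigen test missed. Net inflation is plausible, since the plan uses prior antigen testing to find RT-PCR positives, but its sign and size are not derivable. The only firm figure is the 3.3 points per changed read at 30 per group with one result per participant.

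This does not invalidate the design. It is a cheap improvement that has to be in place before enrolment to be of use.

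**What to change.** Three short additions:

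1. **Bias Minimization and Elimination.** The screener tells each participant, before hand-over, not to mention any prior test result to the operator.
2. **INDICAID Specimen Collection and Testing Procedure.** After recording each INDICAID read, the operator ticks on the Data Collection Form whether the prior result was known or disclosed before that read (yes or no). Placing the question after the read keeps it from prompting the operator beforehand.
3. **Statistical Analysis Plan.** Report PPA and NPA with Wilson intervals for all participants and again without those ticked yes. Label this a descriptive sensitivity analysis and show the number removed from each group.

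Cost: one scripted sentence, one tick box and one table, with no extra staff, swabs or change to standard of care. The second set of estimates will have fewer patients and wider intervals, and the tick box depends on operator honesty and recall. If few or no disclosures are recorded, the form gives the sponsor some evidence that the blind held.

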#### Storage Handling and Shipment

The specimens to be tested on the INDICAID Rapid test shall be tested immediately upon sample collection at the testing site with no storage of the sample. Specimens collected to be tested using the RT-PCR test shall be stored in the following manner:

Temperature Storage	Time Stored
2-8°C	Samples shipped overnight on ice packs within 24 hours of collection

Shipping of biological samples should be done to IATA standards using the appropriate packing materials.

#### INVESTIGATIONAL DEVICE STORAGE AND DISPOSITION

Each site will be responsible for documenting the receipt, maintain proper storage and proper use of the INDICAID Rapid Test kits as prescribed. Any discarded test device shall be documented and remaining test devices returned to Phase Diagnostics.

#### RISK / BENEFIT ANALYSIS

##### Potential Risks Associated with the Study

There is potential risk of exposure to the Coronavirus Disease 2019 and other pathogen to the site operator. The selected site ensures that associated risks are mitigated by employing appropriate state and local safety measures. Refer to the CDC Interim Guidelines for Collecting, Handling, and Testing Clinical Specimens from Persons for Covid-19, <https://www.cdc.gov/coronavirus/2019-nCoV/lab/guidelines-clinical-specimens.html>

### Reporting Adverse Events

No adverse events (AEs) are anticipated for this study. The study is performed entirely *in vitro*. The INDICAID Rapid Test is for investigative use only and labeled accordingly. Test results obtained with the INDICAID Rapid Test are not reported to the appropriate health authorities or used as a diagnosis or determine a treatment method.

If an AE or unanticipated adverse device effect (UADE) occurs during a study, the PI shall report the occurrence to Phase Diagnostics Clinical Affairs within 24 hours of the PI first learning of the event. Phase Diagnostics Clinical Affairs will evaluate the AE or UADE as soon as it is received. Phase Diagnostics will report the AE or UADE according to local and country specific reporting requirements, all governing institutional review boards (IRBs), and all participating PIs.

## DATA AND RECORDS MANAGEMENT

### Study Data and Records Maintenance

According to 21 CFR 812.140(d), Investigators are required to maintain records for a period of two years after the later of the following two dates: (1) the date on which the investigation is terminated or completed or (2) the date that the records are no longer required for purposes of supporting a premarket approval application, a notice of completion of a protocol development protocol, a humanitarian device exemption application, a premarket notification submission, or a request for De Novo classification. Study binders will be provided to each site to organize the required study records and documentation. Each site will be directly responsible for the maintenance and organization of the study documentation. During and after the study, all the information will be submitted to reviewed by Phase Diagnostics to ensure that any missing information is obtained or that any conflicting documentation is resolved.

## MONITORING PLAN

Contact with the PI and study personnel will be maintained by Phase Diagnostic Clinical Affairs representatives primarily the Phase Diagnostic Clinical Study Monitor through periodic site visits, telephone calls, and e-mail. The purpose of site visits will be, verify adherence to the study protocol, and review all study-related documentation and records. A site initiation visit will be conducted to confirm preparedness for protocol execution, confirm satisfactory site facilities, review and clarify regulations and protocol requirements, and train the site personnel prior to activating the site for enrollment. On-site and remote interim monitoring visits will be conducted as needed. A close-out visit will be conducted to ensure all study data and documentation is complete and accurate.

## STATISTICAL METHODS

This section describes the overall approach to data analysis. This proposed design enables evaluation of variance over various factors. All data analysis will be performed in accordance with general principles espoused in CLSI EP12.

## Statistical Analysis Plan

INDICAID COVID-19 Rapid Antigen Test	Reference Test RT-PCR			
		Infected	Not Infected	Total
	Positive	TP	FP	TP+FP
	Negative	FN	TN	FN+TN
	Total	TP+FN	FP+TN	TP+FP+FN+TN

TP = true positive

TN = true negative

FP = false positive

FN = false negative

PPA =  $TP/(TP+FN)$

NPA =  $TN/(TN+FP)$

OPA =  $(TP+TN)/\text{Total Samples}$

The following performance characteristics will be computed: PPA, NPA, OPA and accuracy. The 95% confidence interval for these performance characteristics will be computed using Wilson-Score method.

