## PRODUCT DESCRIPTION AND INTENDED USE

The INDICAID Rapid Antigen Test Kit includes 25 individually sealed single-use Test Devices, 25 Buffer Solution Vials, and 25 sterile Nasal Swabs. A Quick Reference Instruction Sheet is provided with each test kit.

The INDICAID COVID-19 Rapid Antigen Test (INDICAID Rapid Test) is a lateral flow immunoassay (LFA) intended for the qualitative detection of nucleocapsid protein antigen from SARS-CoV-2 in direct nasal swabs from individuals suspected of COVID-19 by their healthcare provider within the first 7 days of symptom onset.

In the USA, testing is limited to laboratories certified under the Clinical Laboratory Improvement Amendments of 1988 (CLIA), 42 U.S.C. §263a, that meet the requirements to perform moderate, high, or waived complexity tests. The INDICAID Rapid Test is intended for use at the Point of Care (POC), i.e., in patient care settings operating under a CLIA Certificate of Waiver, Certificate of Compliance, or Certificate of Accreditation. The test is intended for use by medical professionals or trained personnel specifically instructed and trained in the techniques of in vitro diagnostic procedures and proper infection control procedures, and individuals similarly trained in point of care settings but who are not laboratory professionals.

Positive results are for the identification of SARS-CoV-2 nucleocapsid antigen. This antigen is generally detectable in upper respiratory samples during the acute phase of infection. Positive results indicate the presence of viral antigens, but clinical correlation with patient history and other diagnostic information is necessary to determine infection status. Positive results do not rule out bacterial infection or co-infection with other viruses. The agent detected may not be the definite cause of disease. Laboratories within the United States and its territories are required to report all positive results to the appropriate public health authorities.

Negative results should be treated as presumptive, do not rule out SARS-CoV-2 infection and should not be used as the sole basis for treatment or patient management decisions, including infection control decisions. Negative results should be considered in the context of a patient's recent exposures, history and the presence of clinical signs and symptoms consistent with COVID-19, and confirmed with a molecular assay, if necessary, for patient management.

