#### STUDY OVERVIEW

The purpose of this study is to evaluate the clinical performance of the INDICAID Rapid Test. This will be established by determining the positive percent agreement (PPA), negative percent agreement (NPA), and overall percent agreement (OPA) between the results of the test under investigation and an EUA-approved RT-PCR test, using clinical samples collected from COVID-19 symptomatic individuals. A minimum of 30 RT-PCR SARS-CoV-2 positive and 30 negative patients are required to assess the clinical performance.

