## STUDY DESIGN

### Study Duration

This study will take place across 2 testing sites for 60 days or until patient enrollment targets are met (minimum of 30 RT-PCR SARS-CoV-2 positive and 30 negative patients).

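### Should overall percent agreement stand beside PPA and NPA when enrolment is enriched, and does the undefined term accuracy need repair?

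*Combined protocol and SAP*

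**What the plan says.** The Study Overview says of clinical performance: "This will be established by determining the positive percent agreement (PPA), negative percent agreement (NPA), and overall percent agreement (OPA", and gives the basis as "using clinical samples collected from COVID-19 symptomatic individuals". The Statistical Analysis Plan section sets out a two-by-two table against RT-PCR with row and column totals. It gives formulas for PPA, NPA and OPA, the last as (TP+TN) over all samples. It then states "The following performance characteristics will be computed: PPA, NPA, OPA and accuracy" and adds "The 95% confidence interval for these performance characteristics will be computed using Wilson-Score method". No formula for accuracy appears there or elsewhere.

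Three provisions shape the enrolled mix:

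- Study Duration lets the study run for 60 days or "until patient enrollment targets are met (minimum of 30 RT-PCR SARS-CoV-2 positive and 30 negative patients".
- Sample Enrichment says "In order to enrich for positive patient samples, we will be enrolling patients who have previously been tested", and continues enrolment until 30 positive and 30 negative specimens are in hand.
- The INDICAID testing procedure adds "Each operator shall test a minimum of 3 positives and 3 negatives".

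The intended-use statement concerns swabs "from individuals suspected of COVID-19 by their healthcare provider within the first 7 days of symptom onset". It does not require a prior antigen test.

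**The concern.** PPA and NPA are each conditional on the RT-PCR result, so their arithmetic does not depend on how many positives and negatives are enrolled. OPA does depend on it. If the device is better on negatives than on positives, adding positives lowers OPA and adding negatives raises it, with the device unchanged. Here the mix comes from recruitment: enrichment for positives, two minimums without caps, and a calendar stop as the alternative. Yet the Study Overview puts OPA in the same list as PPA and NPA, and nothing labels it as specific to the sample.

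Two things could be at stake. A reader might take OPA as the agreement to expect in routine use, and it could be too low or too high for that purpose. Also, accuracy is a listed output with no definition, which in principle leaves a choice to be made after the data are seen.

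**Working it through.** **Inputs.** From the documents: the OPA formula, the Wilson method, and the minimums of 30 positive and 30 negative. The documents state no PPA, NPA, prevalence or precision target, so there is no planned figure to reproduce. Assumed for illustration: PPA 85% with NPA 98%, and alternatives as marked.

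**Step 1: the identity.** With s the RT-PCR-positive share of those analysed,

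OPA = s × PPA + (1 − s) × NPA.

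If PPA = NPA, s drops out. At 85%/98%:

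| Positive:negative | s | OPA |
|---|---|---|
| 60:30 | 0.667 | 89.3% |
| 45:30 | 0.600 | 90.2% |
| 30:30 | 0.500 | 0.5 × 85 + 0.5 × 98 = 91.5% |
| 30:45 | 0.400 | 92.8% |
| 30:100 | 0.231 | 95.0% |

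Nothing in the documents suggests that the last mix, or any other very uneven one, is expected.

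**Step 2: how far the mix could drift.** Suppose each enrolled patient is positive independently with chance q, and enrolment stops once both minimums are reached. The 60-day limit and the per-operator minimums are ignored.

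- q = 50%: the chance of exactly 30:30 is C(60,30)/2^60 = 10.3%. The mean total is 66.2, so the larger group averages 36.2. The 5th to 95th percentiles of s are 40.5% and 59.5%. OPA at 85%/98% then runs from 92.7% down to 90.3%, a span of 2.4 points. At 90%/95% it runs from 93.0% to 92.0%.
- q = 2/3: the mean total is 90.0, about 60:30. OPA at 85%/98% runs from 90.7% down to 88.5%.

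**Step 3: compare with sampling error.** For 55 concordant results in 60 (91.7%), the 95% Wilson interval is 81.9% to 96.4%, about 14.5 points wide. The 2.4-point spread from mix is about one sixth of that.

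**Step 4: direction against intended use.** At an assumed intended-use prevalence p,

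crude OPA − OPA(p) = (s − p) × (PPA − NPA).

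At 30:30 with 85%/98%:

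- p = 20%: 0.3 × (−13) = −3.9 points
- p = 30%: −2.6 points
- p = 40%: −1.3 points
- p = 60%: +1.3 points

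The sign reverses when PPA exceeds NPA. At 95%/90% and p = 60% it is (−0.1) × (+5) = −0.5 points, or 92.5% against 93.0%. The direction therefore cannot be stated without knowing both orderings, and the documents give neither.

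**Step 5: is the planned interval sound for what OPA does measure?** Exact enumeration over five PPA/NPA pairs and three mixes (30:30, 60:30, 30:60), 15 scenarios in all, puts Wilson coverage of OPA at its own mix between 94.8% and 97.1%. The interval is adequate.

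**Step 6: accuracy.** In its usual sense it is (TP+TN) over the total. With assumed results of 24/30 and 29/30, OPA is 53/60 = 88.3% (Wilson 77.8% to 94.2%), and accuracy would be the same figure with the same interval.

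**The case for a change.** The best case for a change is that it costs almost nothing. A headline percentage can be quoted without its table. The Study Overview does give OPA a part in establishing performance, and labels are better settled before results are seen. One line could call OPA descriptive of the enrolled sample and print the positive and negative counts beside it, and accuracy could be defined or struck out. The algebra behind this is beyond dispute, and the gap to intended-use agreement (3.9 points at an assumed prevalence of 20%) is larger than the drift from mix alone.

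Most of that stands as a reporting preference; less of it stands as a fault in the plan. The Study Overview lists three measures without ranking them, so equal standing is an inference. No text claims that OPA estimates agreement in routine use. The enrichment is disclosed, and the target is nominally 30:30, although the numbers are minimums. The drift model is itself an assumption: prior antigen results are known at enrolment, so sites could steer towards the unfilled group, while delay in RT-PCR results could add overshoot. A prevalence-weighted OPA would answer a claim the plan does not make. It would need prevalences the documents do not supply, and combining the two Wilson intervals for it gave coverage as low as 92.2% at 30:30 in the scenarios checked. On accuracy, deletion presumes what the sponsor meant, and the likely meaning adds nothing to OPA.

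**Conclusion.** No change follows. OPA does describe the enrolled mix, and it equals intended-use agreement only if PPA = NPA or the enrolled share matches prevalence. That is a matter of reading the figure correctly: the formula, the interval and the data are unaffected. No decision rule in the text depends on OPA, PPA and NPA are reported separately with their own intervals, and the column totals let any reader see the mix or reweight it. Under the assumed 85%/98% and an even chance of a positive, mix alone moves OPA by 2.4 points, small beside an interval about 14.5 points wide; the effect is zero if PPA = NPA. The undefined accuracy is missing detail that an analyst would fill with the usual definition, repeating OPA. These sizes depend on assumed performance and recruitment, but the conclusion does not, because relabelling would leave every computed result as it is. Whether selection on a prior antigen test shifts PPA or NPA themselves is a separate question that relabelling OPA would not touch.
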